### 3 PARTICIPANT SELECTION AND WITHDRAWAL

A total of 200 participants will be recruited for this study and all data will be collected at UNC-CH. No specific plans have been made to enroll participants from vulnerable populations. We will collect data until 48 participants have completed the final session for each phase, and we have estimated 100 participants per phase based on our criteria to progress to future sessions and the relatively large time commitment.

#### 3.1 INCLUSION CRITERIA

In order to be eligible to participate in this study, a participant must meet all of the following criteria:

- Between the ages of 18 and 65
- Right-handed

CONFIDENTIAL

- Able to provide informed consent
- Have normal to corrected vision without color blindness
- Willing to comply with all study procedures and be available for the duration of the study
- Speak and understand English
- Participants will be invited back to the second session only if they are able to perform the task. The criteria for demonstrating the cognitive process of interest is that participants must show a benefit to their working memory percent correct during trials with an informative retro-cue relative to trials with an uninformative neutral cue

### 3.2 EXCLUSION CRITERIA

A potential participant who meets any of the following criteria will be excluded from participation in the study:

- ADHD (currently under treatment)
- Neurological disorders and conditions, including, but not limited to:
  - History of epilepsy
  - Seizures (except childhood febrile seizures)
  - Dementia
  - History of stroke
  - Parkinson's disease
  - Multiple sclerosis
  - Cerebral aneurysm
  - Brain tumors
- Medical or neurological illness or treatment for a medical disorder that could interfere with study participation (e.g., unstable cardiac disease, HIV/AIDS, malignancy, liver or renal impairment)
- Prior brain surgery
- Any brain devices/implants, including cochlear implants and aneurysm clips
- History of current traumatic brain injury
- Failure to pass a colorblindness test
- (For females) Pregnancy or breast feeding
- Anything that, in the opinion of the investigator, would place the participant at increased risk or preclude the participant's full compliance with or completion of the study

**Justifications for any exclusions based on race, gender, or ethnicity:** There are no exclusion criteria based on race, gender, or ethnicity. However, non-English speaking individuals are excluded because the ability to accurately and completely communicate study information, answer questions about the study, and obtain consent are necessary.

**Justification for excluding women or women who become pregnant:** Pregnant participants will be excluded despite the fact that theoretical risk to mother or fetus is exceedingly small, since no safety data for pregnancy is known to exist for TMS studies. Female participants will be asked if there is a possibility that they are pregnant at every stimulation session. If the participant says yes or is unsure, then we will verify pregnancy status via a urine pregnancy test. Only upon a verbal confirmation that pregnancy is not possible or a negative finding will we proceed with the experiment.

### 3.3 STRATEGIES FOR RECRUITMENT AND RETENTION

#### 3.3.1 RECRUITMENT

The target population of this study includes healthy individuals between the ages of 18 to 45 recruited from UNC Chapel Hill and the surrounding area, including approximately 30,000 candidates for participation.

Recruitment will occur via two methods: flyers to be distributed at major locations on the campus (libraries, gyms, classroom buildings, etc.) and a mass email to all individuals with a UNC-affiliated email address.

---

### 3.3.2 RETENTION

Our retention strategy includes a payment schedule of one time per session per participant. The payment amount per hour increases with each session to encourage study completion. The participant will receive payment at the end of each session. The research staff will also give each participant a reminder call or email for upcoming sessions. Each research staff member will be available for the participants to contact via email or phone.

#### 4 BASIC STUDY DESIGN

This study is a pilot, five-session study with transcranial magnetic stimulation (TMS), electroencephalography (EEG), and magnetic resonance imaging (MRI) to understand the neural oscillatory basis of output-gating. The first session of the experiment will be screening session, in which participants provide written consent to participate, screened for colorblindness, complete questionnaires, and perform a working memory task with retrospective cues. Participants will be invited back to the second session if they show a benefit to their working memory percent correct by use of the informative retro-cue relative to the uninformative neutral cue. This session will also be used to select the number of items that will be used in the working memory task for subsequent sessions. The criteria for difficulty titration is task performance between 60% and 85% correct for retro-cue trials and a benefit of at least 5% greater than neutral cue trials. Thus, different participants will perform the task with different numbers of items to be encoded into working memory. Titration of task difficulty as described here is critical for experiments that use causal manipulation (e.g. transcranial magnetic stimulation) to modulate performance. If participants are performing at ceiling (close to 100%) or at floor (close to random chance), then any experimental manipulation of behavior is less likely to impact performance as the task is too "easy" or too "hard." For the second session of the experiment,

[figure not shown]

Fig1. Experimental design consists of five sessions. The two phases of the experiment randomize and counterbalanced different parameters of stimulation for the 4th and 5th session. w/ = with. WM = working memory.

participants perform the working memory retro-cue task while EEG is recorded. In addition, participants will complete a simple perception color task in which participants see a color and choose the matching color from the color circle. This task tests for the precision of perception throughout the color circle. The EEG data from the second session will be preprocessed and a Morlet wavelet convolution analysis will be conducted. The resulting spectrogram will be contrasted between the informative retro-cue and uninformative neutral cue to derive the theta frequency with peak amplitude in

prefrontal cortex, and contrasted between a leftward and rightward retro-cue to derive the alpha frequency with peak amplitude in parietal cortex. These peak frequencies will be used for stimulation in the fourth and fifth session. In the third session, we will acquire a structural MRI and resting-state scan (10 minutes) for each participant. The resting-state functional MRI data will be analyzed using independent component analysis. This technique will identify regions in the anterior middle frontal gyrus and posterior intraparietal sulcus that are functionally connected within the frontal-parietal, "executive control," network. A previous meta-analysis of functional MRI studies found that the regions with peak retro-cue activity was at Montreal Neurological Institute coordinates (-40, 36, 28) for anterior middle frontal gyrus and (-38, -48, 44) for inferior intraparietal sulcus. Therefore, we will constrain our search lights to the anatomical landmarks and these coordinates. The center of mass in these regions will be used for targeting

CONFIDENTIAL

with TMS in the subsequent fourth and fifth sessions. In the fourth and fifth sessions, stimulation will be delivered at the timing relative to retro-cue, frequency, and spatial location based on our previous localizers. During stimulation, the location of the TMS coil needs to be aligned to the targeted brain region with neuro-navigation software that records the accuracy of each TMS pulse relative to the target (Localite, Sankt Augustin, Germany). On each trial, the stimulation type will be randomly selected, counter-balanced, and inter-mixed (see section 4.1 below). The effects of rhythmic TMS are not expected to last for more than a few cycles beyond stimulation itself (Thut et al. 2011; Hanslmayr et al. 2014; Albouy et al. 2017). Therefore, the experimental design randomly intermixes the stimulation type within every task block.

#### 4.1 TREATMENT ASSIGNMENT PROCEDURES

Phase one: Participants will receive stimulation to either the frontal or parietal cortex in a randomized and counter-balanced sequence for the fourth and fifth session. Randomization and counterbalancing is performed by a script that generates a spreadsheet to stimulation ID mapping. Participants are randomized upon entering the fourth session of the experiment. Thus, there is no influence of the experiment on which sequence the participant will receive. Stimulation types are randomized and counter-balanced by a script at the time of the session and defined as theta, alpha, arrhythmic-theta, and arrhythmic-alpha. It should be noted that all analyses are controlled by a within-session contrast that accounts for general sequence effects.

Phase two: Participants are randomized to receive stimulation to both the frontal and parietal cortex in either theta or alpha frequency for both of the fourth and fifth session. A similar randomization procedure will be used as in phase one. Stimulation types are randomized and counter-balanced within a session by a script: in-synchrony, anti-synchrony, arrhythmic-synchrony, and arrhythmic-independent. It should be noted that all analyses are controlled by a within-session contrast by comparing to arrhythmic stimulation.

The primary analysis of the experiment is controlled within-session as a contrast with the arrhythmic control conditions. The difference in site of stimulation for phase one and the auditory difference between theta and alpha stimulation (theta is audibly slower than alpha) precludes double-blinding as the researcher will be aware of this difference in running the experiment. In other words, the study cannot be blinded and there is no attempt to blind the study. Furthermore, the control for each stimulation condition is self-contained within each session. The stimulation sessions for each phase consists of four stimulation conditions (described above) and two task conditions (retro-cue to the left visual field and retro-cue to the right visual field), thus there are a total of 8 conditions total for phase 1 and 4 conditions total for phase 2. With 600 trials per session, then will be 75 trials of each condition for phase 1 and 150 trials of each conditions for phase 2. The order of these trials is randomized for each session for each participant via a script.

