with a random inter-pulse interval that lasts the same duration as the alpha train of pulses. The duration of the trains is matched to control for non-frequency-specific effects of TMS. The minimum inter-pulse interval will be 20 milliseconds. Between every train will be at least 5 seconds. An inter-train-interval of 5 seconds or greater allows for any residual effects of stimulation to return to baseline. This intensity, inter-pulse-interval, and inter-train-interval is well within the safety guidelines set forth for repetitive TMS (Wassermann, 1998; Rossi et al., 2009) and has been used in similar paradigms as the one described here (Thut et al. 2011; Hanslmayr et al. 2014; Albouy et al. 2017). For phase one, participants receive trains to either frontal or parietal cortex for each stimulation session (session 4 and 5). For each session of phase one, participants receive trains in theta, alpha, arrhythmic-theta, and arrhythmic-alpha. For phase two, participants receive trains to both frontal and parietal cortex in both sessions (session 4 and session 5) using two TMS coils. In session 4 and session 5, participants will receive stimulation in either theta or alpha frequency. For each of sessions 4 and 5 of phase two, participants receive trains in-synchrony (five pulses delivered to both sites at the same time), anti-synchrony (five pulses delivered to each site with a 180-degree phase difference), arrhythmic-in-synchrony (five pulses delivered to both sites at the same time), and arrhythmic-independent (five pulses delivered to both sites randomly without any temporal relation). Theta frequency functional connectivity is hypothesized to play a causal role in the prioritization and suppression of working memory representations. Alpha frequency stimulation is included as a control to test for the frequency specificity of functional connectivity.

EEG will be collected using the Geodesic 400 system (EGI INC., Eugene, OR, USA). Collecting simultaneous EEG and TMS does not pose any additional risk over TMS on its own. EEG does not involve brain stimulation and is used purely for neuroimaging (minimal risk).

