### Session 4 and 5: Stimulation 1 and 2 (3 hours)

- Motor thresholding using single pulse TMS for use in future sessions will be performed once for each participant on the first day of stimulation, and held constant for the following stimulation session.
- Before practice and performance of the cognitive control task, the TMS coils will be positioned over the targeted region.
- During performance of the task, stimulation will be delivered on every trial.

CONFIDENTIAL

- During stimulation, white noise will be played for the participants to reduce neural effects of auditory entrainment of rhythmic TMS.
- At the end of the session, participants will receive \$40, and \$60 in compensation for sessions 4, and 5, respectively.

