### 11.1 STATISTICAL ANALYSIS STRATEGIES

The statistical analysis plan below aligns with the aims that are described in Section 2.3. all statistical estimates of population parameters will be tabulated along with corresponding confidence intervals (CIs) to convey levels of precision / imprecision. All hypothesis tests that yield large p-values ( $p>0.05$ ) will be reported as being inconclusive.

*Phase One* overarching goal: Investigate the causal role of frontal theta and parietal alpha oscillations in the prioritization and suppression of working memory representations. To control for non-specific effects of rhythmic TMS, we will use an active control: arrhythmic TMS (randomized inter-pulse-interval) that is matched to the target stimulation in number of pulses and temporal duration. All analyses will be performed on the difference from condition-matched arrhythmic TMS. The key analyses are built upon a three-way parallel arms design: with factors TMS frequency (theta versus alpha), location (frontal versus parietal), and cue direction (left versus right retro-cue). There is an equal number of trials for each of these conditions and there are 75 trials for each condition per participant.

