Aim 1 (primary outcome): Stimulation that is aligned to the endogenous activity of the brain (frontal theta and parietal alpha) is hypothesized to improve performance whereas the mismatched frequency of stimulation is hypothesized to decrease performance (frontal alpha and parietal theta). Performance is assessed using Pashler's working memory capacity metric ( $k$ ) which is defined as:  $k = N * \frac{HR*FA}{1-FA}$  where  $N$  is the number of the items that are held in memory. HR is the hit rate defined as the percent correct for trials where the probe does not match the encoding array. FA is the false alarm rate defined as the percent incorrect for trials where the probe does match the encoding array. We will perform a two-way repeated-measures ANOVA with two within-participant factors TMS site (frontal or parietal) and TMS frequency (theta or alpha). We expect to observe a small p-value ( $p < 0.05$ ) for the interaction between TMS site and TMS frequency. Post-hoc t-tests will be performed using Tukey's method to control for multiple comparisons. *Sensitivity analysis*: In addition to calculating changes in working memory capacity, the impact on hit rate, false alarm rate, and overall accuracy will be calculated. The robustness of these effects will be estimated using an individual differences analyses where baseline performance is used as a covariate to improve model estimation. Finally, the titration of working memory load by participant will be added as a covariate to explore if this factor changes the model estimation. These are framed as exploratory analyses.

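### If phase-one site varies within participants, a session change specific to theta minus alpha stays in the site-by-frequency test, and the randomised order is not in the model

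*Combined protocol and SAP*

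**What the plan says.** **Schedule.** Section 4.1, phase one: "Participants will receive stimulation to either the frontal or parietal cortex in a randomized and counter-balanced sequence for the fourth and fifth session". Section 2.2: "For each session of phase one, participants receive trains in theta, alpha, arrhythmic-theta, and arrhythmic-alpha". Section 4 adds that "the experimental design randomly intermixes the stimulation type within every task block". Each session therefore has one site, both frequencies and both matched arrhythmic controls.

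**Analysis.** Section 11.1: "All analyses will be performed on the difference from condition-matched arrhythmic TMS". Aim 1 specifies a "two-way repeated-measures ANOVA with two within-participant factors TMS site (frontal or parietal) and TMS frequency (theta or alpha"), and the test of interest is the interaction: "We expect to observe a small p-value ( $p < 0.05$ ) for the interaction between TMS site and TMS frequency". Aims 2, 3 and 5 use the same site-by-frequency ANOVA. None of the four includes session, period or order. The Aim 1 sensitivity analyses add only baseline performance and memory load as covariates.

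**Order.** On order, section 4.1 relies on the within-session contrast: "It should be noted that all analyses are controlled by a within-session contrast that accounts for general sequence effects".

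**Design label.** The Study Summary and the phase-one paragraph of section 11.1 call the design parallel arms. The version 7.0 entry in section 1.5 records a move from crossover to parallel arms.

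**The concern.** Site and session change together within each person, and only the randomised order separates them. The interaction score is a frontal-session quantity minus a parietal-session quantity. Subtracting the arrhythmic control inside each session cannot remove a change between sessions in the very quantity being compared, theta minus alpha.

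Counterbalancing without an order term turns such a change into error variance. If the two orders are unequal among those analysed, part of it becomes bias. Participants are randomised on entering session 4 (section 4.1), while the target of 48 counts people who completed the final session (section 3). Losses between the two sessions could therefore unbalance order, and nothing in the documents enforces balance among completers.

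Two primary outcomes (Aims 1 and 2) and two secondary ones (Aims 3 and 5) rest on this test.

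**Working it through.** **Inputs.** From section 11.2: effect size 0.532 for the site-by-frequency interaction, 95% power, n = 48. From section 11.1: significance level 0.05. Assumed, because the documents do not say: a two-sided test, 0.532 as the standardised mean of the within-person interaction score (SD 1), the values of d, and the order splits.

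**The plan's own figure.** A one-sample t-test on the interaction score with standardised mean 0.532 first reaches 95% power at n = 48 (power .9505). The same method returns the other two sample sizes in section 11.2: 21 for 0.83 and 44 for 0.56. So 0.532 behaves as a paired effect, which agrees with site being within participants.

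**The score.** For one participant, let

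t(site) = (theta − arrhythmic-theta) − (alpha − arrhythmic-alpha), measured in that site's session.

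The interaction score is t(frontal) − t(parietal).

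**What cancels and what does not.**

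1. A shift common to all trials of a session cancels inside each rhythmic-minus-arrhythmic difference. Simulated shifts of 1 and 5 SD left bias within 0.003 of zero and type I error at 4.9% to 5.5%, at 24/24 and 28/20.
2. A session change in rhythmic minus arrhythmic that is the same for theta and alpha cancels in theta minus alpha. Simulated bias was about zero and type I error 4.7% to 5.0%.
3. A session-5 change of size d in theta minus alpha does not cancel. It enters as −d for frontal-first and +d for parietal-first participants; the sign convention is arbitrary.

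**Balanced order, 24/24.** The mean shift is (24d − 24d)/48 = 0, and the SD of the score rises to about √(1 + d²).

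| d (assumed) | SD of score | Power, no order term | Type I error, no order term | Power, with sequence |
|---|---|---|---|---|
| 0 | 1.00 | .95 | 5% | .95 |
| 0.25 | 1.03 | .94 | 4% to 5% | .95 |
| 0.5 | 1.12 | .92 | 3% | .95 |
| 1 | 1.42 | .79 | 0.6% | .95 |

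**Unequal order, 28/20.** The bias is d × (28 − 20)/48 = 0.17d in size. For d of 0.25, 0.5 and 1 that is 0.04, 0.08 and 0.17. Type I error without the term is 5% to 6%. If the bias opposes the effect, power is .90, .80 and .39, against about .94 with sequence in the model. If it runs with the effect, the interaction is overestimated by the same amount.

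**A more uneven case, 30/18.** The bias is d × 12/48 = 0.25d. At d = 0.5 the type I error is about 9% without the term and 5% with it.

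**Cost when d = 0.** Error degrees of freedom go from 47 to 46. At 24/24, exact power goes from .9505 to .9503.

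**The case against.** The strongest reply is that section 4.1 claims only that general sequence effects are dealt with, and for this test that is right. All four trains are intermixed in every session, so the score is a difference of within-session differences, and steps 1 and 2 show that general effects drop out. This stands. A reader might infer that session effects as a whole remain in the primary test, or that the section 4.1 sentence is false. The documents support neither.

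A reader might also name practice, habituation or motor thresholding as the cause, since thresholding "will be performed once for each participant on the first day of stimulation". None of these is frequency-specific on its face, and the threshold is then held constant. Even a proportional change does little under the plan's hypothesis. If session-5 effects are multiplied by c, the frontal-first score is t(frontal) − c·t(parietal) and the parietal-first score is c·t(frontal) − t(parietal). The gap between them is (1 − c)·[t(frontal) + t(parietal)]. Aim 1 expects the two t values to have opposite signs, so the gap is small, and it is zero if they are equal in size. No passage points to a frequency-specific session change. This also stands: d may be near zero.

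The larger figures above need a large d: 0.5 is close to the whole hypothesised effect of 0.532. Order is randomised and counterbalanced at session 4, so earlier losses cannot unbalance it. Only dropout between sessions 4 and 5, about a week apart, could.

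Last, if phase-one site is really parallel, site does not change between sessions, and neither the mechanism nor a frontal-first/parietal-first factor exists. Phase two was plainly rewritten this way: frequency is between participants in section 4.1 and Aim 6. Phase one still has a site sequence in section 4.1 and a within-participant site factor in Aim 1. The documents do not settle which is meant.

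None of this explains why a randomised design feature, known before analysis, is left out of the model when including it costs almost nothing.

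**Conclusion.** The point holds in a narrow form, conditional on site being within participants in phase one. The within-session contrast deals with additive session effects and with changes common to both frequencies. It does not deal with a session change specific to theta minus alpha, and the Aim 1, 2, 3 and 5 models have nothing else that does.

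At 24/24 the consequence is lost precision without bias, and the test becomes conservative. A reader might infer an inflated false-positive rate. At 24/24 there is none, and at 28/20 it is at most about 6%; the 9% figure needs both a 30/18 split and d = 0.5. Bias arises only with unequal order among completers.

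The values of d and the splits are assumptions that show the range of consequences; they are not estimates. This is a cheap improvement to specify before analysis, not a flaw that undermines the trial.

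**What to change.** 1. **Settle the design first.** Reconcile the parallel-arms wording in the Study Summary and section 11.1 (and the version 7.0 entry in section 1.5) with section 4.1 and Aim 1. If phase-one site is between participants, the steps below do not apply, and the section 4.1 sentence on sequence and the within-participant site factor in Aim 1 need rewriting instead.
2. **If site is within participants,** add randomised sequence (frontal-first or parietal-first) to the Aim 1, 2, 3 and 5 models as a between-participant factor with all its interactions. The sequence-by-site-by-frequency term, equivalent to session by frequency, is the one that removes d; a sequence main effect alone would not.
3. **Test site by frequency as the equal-weight average of the two sequences,** so that unequal numbers do not bias it.
4. **Narrow the section 4.1 sentence:** the within-session contrast removes additive session effects and those common to both frequencies, and the sequence term removes frequency-specific ones.
5. **Report the number analysed in each order.**

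The cost is one error degree of freedom (47 to 46) and a few lines of text. N stays 48 and power stays about .95 at 24/24.
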